6.1.1. Analysis of Adverse Events

Adverse events will be coded using MedDRA version 20 (June 2017).

All AE tables will be summarized by SOC and PT by treatment group, including the number of patients for each SOC and PT. Within each patient, multiple records of events mapping to a common MedDRA PT and SOC will be condensed into a single AE for incidence counts. Adverse Events will be reported by SOC and by PT in decreasing order of the highest active dose group of study medication (i.e 6.0 mg).

Listings of patients who discontinue the study for an AE, patients who experience an SAE and patients with AEs resulting in death will be presented.

6.2. Clinical Laboratory Evaluations

- Change from baseline to Week 1 (Visit 3) in laboratory parameters
- Change from baseline to End of Study (Visit 6) in laboratory parameters

Laboratory parameters to be analyzed are:

- Hematology: hemoglobin, hematocrit, total white cell count, leukocyte differential count and platelet count
- Biochemistry: creatinine, total bilirubin, alkaline phosphatase, aspartate aminotransferase, alanine transaminase, gamma-glutamyl transferase, lactate dehydrogenase, creatine kinase, thyroid stimulating hormone, triiodothyronine and

thyroxine, glucose, potassium, sodium and calcium

- Urinalysis: leukocytes, blood, ketones, bilirubin, urobilinogen, protein and glucose.

6.2.1. Analysis of Clinical Laboratory Evaluation

Descriptive statistics (number of observations, mean, standard deviation, minimum, median and maximum values) for collected values and change from baseline will be summarized for clinical laboratory tests (hematology, biochemistry and urinalysis) at applicable visits, by treatment groups.

Selected laboratory test results will be classified by markedly abnormal criteria as normal or abnormal, according to Table 3 below. The number and percentage of patients with markedly abnormal laboratory results will be provided. No statistical testing will be performed on laboratory data.

Table 3: Markedly abnormal ranges for clinical laboratory parameters

Parameter	Markedly Abnormally High Criteria
Alanine Amino Transferase (ALT)	>3 times Upper Limit of Normal Range
Alkaline Phosphatase	>3 times Upper Limit of Normal Range
Aspartate Amino Transferase (AST)	>3 times Upper Limit of Normal Range
Creatinine	221 $\mu\text{mol/L}$
Gamma Glutamyl Transferase (GGT)	>3 times Upper Limit of Normal Range
Total Bilirubin	>3 times Upper Limit of Normal Range

In addition, abnormal values (relative to the normal range) for hematology and biochemistry will be presented by treatment, patient, visit, and parameter in data listings (including all values of a parameter if at least one value was abnormal per patient). These listings will include: treatment, subject identifier, the laboratory parameter, units, visit number and study day, parameter value, an indicator for values outside of the reference range (H or L), the reference range, and an indicator for clinically significant out-of-range values.

All laboratory parameter results will be listed.

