4 SELECTION OF STUDY POPULATION

4.1 Inclusion Criteria

Eligible patients must meet all of the following criteria:

- 1. Sign an informed consent document indicating they understand the purpose of and procedures required for the study and are willing to participate.
- 2. Male or female aged between 40 and 75 years inclusive, at the time of informed consent.
- 3. If male: unless surgically sterile, must agree to meet the following from the first dose up to the Telephone Follow-up, 2 weeks after the last dose of study medication: □ Not donate sperm
 - *Either:* be sexually abstinent in accordance with a patient's usual and preferred lifestyle (but agree to abide by the contraception requirements below should their circumstances change)
- Or: use a condom with all sexual partners. If the partner is a female of childbearing potential the condom must be used with spermicide and a second reliable form of contraception must also be used (e.g. diaphragm/cap with spermicide, established hormonal contraception, intra-uterine device)

If female: be of non-childbearing potential, or use a highly effective form of contraception as defined in Appendix I. All female patients of childbearing potential must use this contraceptive from first dose until the Telephone Follow-up (2 weeks after final dose) and have a negative pregnancy test at Visit 1 and Visit 2 prior to randomization.

- 4. Have a 12-lead ECG recording at screening (Visit 1) showing the following (and no changes at Visit 2 deemed clinically significant by the Investigator): ☐ Heart rate between 50 and 90 beats per minute
 - QT interval corrected for heart rate using Fridericia's formula (QTcF) interval ≤450 msec for males and ≤470 msec for females
 - QRS interval ≤120 msec
 - PR interval <200 msec
 - No clinically significant abnormality including morphology (e.g. left bundle branch block, atrioventricular nodal dysfunction, ST segment abnormalities consistent with ischemia).
- 5. Capable of complying with all study restrictions and procedures, including ability to use the study nebulizer correctly.
- 6. Body mass index (BMI) between 18 and 35 kg/m² (inclusive) with a minimum weight of 45 kg.
- 7. COPD diagnosis: Patients with a diagnosis of COPD as defined by the American Thoracic Society (ATS)/European Respiratory Society (ERS) guidelines (Celli and MacNee, 2004) with symptoms compatible with COPD for at least 1 year prior to screening (Visit 1).

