Average EXACT-PRO total scores, average daily use of rescue medication, SGRQ-C total scores, MRC, global assessment of change, and TDI scores will be compared between the five treatments using ANCOVA models with treatment and country(/center) as factors and using baseline as a covariate where appropriate. Subdomain scores of the EXACT-PRO and SGRQC will be summarized and subjected to exploratory analyses.

The number of COPD exacerbations will be summarized by treatment group.

Testing for efficacy will start with the highest dose of RPL554 versus placebo. If a statistically significant difference is found, the testing will proceed with the next highest dose, and so on. Secondarily, the various doses of RPL554 will be compared. Appropriate measures will be taken to control for the type I error rate in these hypothesis tests. A closed testing procedure to test active dose vs. placebo will be used for the primary endpoint. The study is not powered for pairwise differences between active doses. Thus, dose-response is best investigated in a secondary analysis fitting an appropriate dose-response model to the data. The Statistical Analysis Plan will provide additional details of the multiplicity adjustment method(s) used.

All hypothesis testing will be done using two-sided alternative hypotheses. P-values less than 5% will be considered statistically significant.

9.2.2.6 *Safety*

Safety data, including safety laboratory tests, ECG parameters, Holter monitors, vital signs and physical examinations, will be summarized by treatment group and time point, when appropriate. For continuous variables, the change from baseline (both regarding pre-dose at Visit 2 and pre-dose at each treatment visit) to each post-dose time point will also be calculated and summarized. Data will further be illustrated by shift tables (showing changes from low/normal/high) and shift plots for selected time points.

Coded adverse event terms will be presented by system organ class (SOC) and preferred term and summarized by treatment group. A summary table by treatment group with total number and number of patients with adverse events, SAEs, adverse events leading to discontinuation of study medication, causally related adverse events and severe adverse events will be produced. Further SAEs, causally related adverse events and adverse event of each intensity will be summarized by SOC and preferred term.

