6.3.1. Analysis of ECG Evaluations

A 12-lead ECG will be recorded at Baseline and Screening, visits 2, 3, 4, 5 and end of study (or

early termination). The overall ECG investigator interpretations will be summarized using a shift table comparing Baseline to time points. The ECG interpretations will be reported as “Normal”, “Abnormal NCS (Not Clinically Significant)”, or “Abnormal CS (Clinically Significant)”. The denominators for the percentages will be the numbers of patients with ECG data at both the baseline and at the time point in question in each treatment group. The quantitative parameters listed in 6.3 will be summarized and listed.

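### The SAP leaves out, without declaring it, the protocol's low/normal/high safety shift tables, so most laboratory abnormalities and all QTcF, PR and QRS outliers get no patient count by dose

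*SAP*

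**What the plan says.** **Protocol 9.2.2.6 (Safety).** The scope is wide: "Safety data, including safety laboratory tests, ECG parameters, Holter monitors, vital signs and physical examinations, will be summarized by treatment group and time point". It then adds: "Data will further be illustrated by shift tables (showing changes from low/normal/high) and shift plots for selected time points". It does not name parameters or visits for the shift tables.

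**SAP 6.2.1 (laboratory).** Every test is summarized by treatment group and visit with "Descriptive statistics (number of observations, mean, standard deviation, minimum, median and maximum values) for collected values and change from baseline". Categories are limited: "Selected laboratory test results will be classified by markedly abnormal criteria as normal or abnormal, according to Table 3 below". Table 3 has a single criteria column, headed "Markedly Abnormally High Criteria", for ALT, alkaline phosphatase, AST, creatinine, GGT and total bilirubin. The count follows from it: "The number and percentage of patients with markedly abnormal laboratory results will be provided". Out-of-range hematology and biochemistry values go into listings by treatment and patient, flagged H or L, with a marker for clinical significance.

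**SAP 6.3 and 6.3.1 (ECG).** For QTcF, QRS, PR, RR and heart rate: "The quantitative parameters listed in 6.3 will be summarized and listed". Under SAP 3.7 that means n, mean, SD, median, minimum and maximum. The one ECG shift table is for the investigator's overall interpretation.

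**SAP 3.4 (changes).** Two items are declared: the move from LOCF ANCOVA to MMRM, and the new Per-Protocol set. The shift tables are not mentioned.

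**The concern.** Describing how safety depends on dose is part of the study's purpose (protocol 3.2), and laboratory tests and 12-lead ECG including QTcF are secondary safety endpoints (protocol 9.2.1.2). A dose comparison of uncommon individual excursions needs a numerator for each arm. Carried out as written, the SAP gives no such number for low potassium, for high or low glucose, calcium or sodium, for any hematology item, or for a long QTcF, PR or QRS.

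The protocol gives some reason to want these counts. It reports a small heart-rate increase after a week of 12 mg twice daily in COPD patients (5.4.1), and it names hypokalemia and tachycardia as known albuterol effects (1.1). All patients are supplied with albuterol (5.9.1). The on-treatment ECG at 2 hours falls soon after the reported time of peak concentration, 1 to 1.5 hours (1.1), so it is reasonably placed to show an individual QTcF change.

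The omission is also undeclared. Protocol 9.1 requires departures from the protocol's analysis to be detailed and justified in the study report, and one that SAP 3.4 does not list is easily missed.

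**Working it through.** **1. The plan's own figure, used here only for arm size.** Protocol 9.3 and SAP 3.3 give SD 250 mL, difference 111 mL, two-sided 5% and 80% power. n = 2 × (1.960 + 0.842)² × 250² / 111² = 79.6, so 80 per group, as stated. Nothing else below depends on this calculation.

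**2. Planned and delivered, side by side.**

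| Data | Protocol 9.2.2.6 | Patient counts by group in the SAP |
|---|---|---|
| Hematology, biochemistry | Within scope of low/normal/high shift tables and plots | Table 3 only: six analytes, high side |
| QTcF, PR, QRS | Within the same paragraph's scope | None by value or change |
| Overall ECG reading | Within the same scope | Shift table of the investigator's interpretation; clinically significant abnormality |
| Holter | Within the same scope | Patients with runs, including new runs (6.3.2) |
| Blood pressure, heart rate, weight | Within the same scope | Low and high criteria (Table 4) |

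**3. Laboratory coverage, counted from SAP 6.2.**
- Hematology has 5 items (the leukocyte differential taken as one) and biochemistry 15, so 20 in all.
- Table 3 covers 6 biochemistry items and no hematology item.
- Without a counted category: 20 − 6 = 14. These are the 5 hematology items plus LDH, creatine kinase, TSH, T3, T4, glucose, potassium, sodium and calcium.
- Low-side criteria: 0.

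**4. What the planned summary can and cannot show (illustration).** The outlier rates, the 60 msec rise and the SDs of change are assumptions; the documents give none of them.
- At true outlier rates of 1%, 2.5% and 5%, the expected number per arm of 80 is 0.8, 2 and 4. The chance of at least one, 1 − (1 − p)^80, is 0.55, 0.87 and 0.98.
- If k of 80 patients have a QTcF rise of 60 msec, the arm mean moves by 60k/80: 0.75 msec for k = 1, 1.5 for k = 2, 3.0 for k = 4.
- The standard error of a difference between two arms is SD × √(2/80): about 1.6, 2.4 and 3.2 msec for SDs of 10, 15 and 20 msec. The shift for k = 2 is 0.95, 0.63 and 0.47 of a standard error; for k = 4 it is 1.90, 1.26 and 0.95.
- The maximum would be about 60 msec whether k is 1 or 4. It shows that someone was affected, not how many.
- A count would separate 1/80 (1.25%) from 4/80 (5%).

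**The case against.** The strongest reply is that the SAP gives more than it may seem to, and most of that reply stands.

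- **Not means only.** A reader might infer that QTcF and most laboratory tests are reported as group means alone. The documents do not support that: SD, median, minimum and maximum are tabulated, for values and for changes.
- **Not invisible.** A reader might also infer that outliers cannot be seen. The expected maximum of 80 normal values is about 2.4 SD, or 24, 36 and 48 msec for SDs of 10, 15 and 20 msec. A 60 msec change would exceed all three. Listings also show each patient, with two-sided H/L flags for hematology and biochemistry.
- **Other counts remain.** Clinically significant ECG abnormality, the overall ECG shift table, Holter runs, adverse events and Table 4 heart-rate outliers are kept. Heart rate is therefore largely covered. None of these is specific to QTcF, PR, QRS or low laboratory values.
- **The clinical background is modest.** The heart-rate increase was at twice this study's top dose. Protocol 1.1 names hypokalemia as an albuterol effect and says RPL554 had fewer such effects. On-treatment laboratory samples are pre-dose (6.4.1, 6.5.1), and short-acting bronchodilators are withheld for at least 8 hours before visit spirometry (5.9.1), so a potassium shift table is a weak detector of acute, rescue-related falls.
- **The protocol does not promise everything.** It speaks of selected time points and does not name every parameter at Weeks 1 and 4. Protocol 9.1 also calls its statistical text a summary.
- **Entry limits are not analysis cut-offs.** It is tempting to count patients against inclusion criterion 4 ("QT interval corrected for heart rate using Fridericia's formula (QTcF) interval ≤450 msec for males and ≤470 msec for females"). The documents give those limits only as eligibility criteria at screening.

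What the reply does not meet is the core: a planned form of summary is absent for laboratory and numeric ECG data, the absence is undeclared, and neither extremes nor listings give a number of patients by dose. Table 4 shows that the SAP accepts two-sided outlier counts for vital signs.

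**Conclusion.** The point holds as an undeclared omission and a gap in counting. Of 20 hematology and biochemistry items, 14 have no abnormality count and none has a low-side count; QTcF, PR and QRS have no categories. Individual outliers remain visible as extremes and in listings, but nobody can read from the planned tables how many patients at each dose were affected.

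The text comparison and the item counts rest on no assumption. The illustration rests on an assumed 60 msec rise, assumed outlier rates of 1% to 5% and assumed SDs of 10 to 20 msec; it shows only that a few affected patients barely move a mean and that a maximum does not count them. No efficacy result, error rate or sample size is affected. This is an inexpensive improvement that the SAP should make, not a flaw that undermines the trial.

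**What to change.** 1. **SAP 6.2.1:** restore baseline-to-post-baseline low/normal/high shift tables by treatment for hematology and biochemistry, using the reference-range flags already planned for the listings. In the schedule of assessments, laboratory samples are taken at screening, Week 1 and Week 4, so baseline will normally be the screening sample and there are two on-treatment time points. State which time points, if any, get shift plots.
2. **SAP 6.3.1:** add n (%) of patients by arm and visit in QTcF value categories and change-from-baseline categories, and PR and QRS if wanted. The sponsor should set the cut-offs before unblinding and say where they come from. If unblinding has already happened, label the tables as added afterwards.
3. **SAP 3.4:** if any of the protocol's shift tables or plots is dropped on purpose, list it with the reason.

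The cost is SAP wording and a few extra descriptive tables from data the SAP already plans to list. No new data collection or hypothesis test is needed.

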6.3. Electrocardiograms

- Change from baseline (pre-dose at Visit 2) to 2-hours post-dose at Day 1, Week 1, Week 2, Week 3 and End of study in ECG parameters
- Change from pre-dose to 2-hours post-dose at Week 1, Week 2, Week 3 and End of study in ECG parameters
- Clinically significant ECG abnormality during treatment period

ECG parameters to be analyzed are: QTcF Interval (msec), QRS Interval (msec), PR Interval (msec), RR (msec) and Heart rate (bpm).

6.3.1. Analysis of ECG Evaluations

A 12-lead ECG will be recorded at Baseline and Screening, visits 2, 3, 4, 5 and end of study (or

early termination). The overall ECG investigator interpretations will be summarized using a shift table comparing Baseline to time points. The ECG interpretations will be reported as “Normal”, “Abnormal NCS (Not Clinically Significant)”, or “Abnormal CS (Clinically Significant)”. The denominators for the percentages will be the numbers of patients with ECG data at both the baseline and at the time point in question in each treatment group. The quantitative parameters listed in 6.3 will be summarized and listed.

6.3.2. Holter Monitors

- Change from screening to Week 4 in Holter parameters

The following parameter will be summarized:

Atrial Fibrillation Time in %, Supraventricular, Supraventricular Couplets, Supraventricular Runs, Ventricular Single, Ventricular Couplets, Ventricular Runs, Number of RR > 2 seconds
The number of patients with Supraventricular or Ventricular runs, and the total number of runs will be also summarized at Screening and Week 4, presenting also the number of patients who had no runs at screening but had run at Week 4.

These parameters will also be listed together with the start and stop of Holter recording.

6.4. Vital Signs

- Change from baseline (pre-dose at Visit 2) to each post-dose assessment at Day 1, Week 1, Week 2, Week 3 and Week 4 in vital signs parameters
- Change from pre-dose to each post-dose assessment at Week 1, Week 2, Week 3 and Week 4 in vital signs parameters

Blood pressure (systolic and diastolic) and pulse rate will be measured at screening (visit 1) and pre-dose, 30 minutes and 1, 2, 4, 6, 8 and 12 hours post-dose at visits 2 and 6.

Blood pressure and pulse rate will be measured at pre-dose and 30 minutes, 1, 2 and 3 hours after dosing at visits 3 to 5.

6.4.1. Analysis of Vital Signs

Vital signs to be analyzed and presented are body weight, sitting blood pressure (systolic and diastolic), sitting pulse rate, and BMI. Vital signs at all study visits and changes from baseline at post-baseline visits will be summarized by visit for each treatment group using descriptive statistics.

Post-baseline results qualifying as Markedly Abnormal will be summarized by treatment group by parameter. Post-baseline markedly abnormal vital signs criteria are defined below:

Table 4: Markedly Abnormal Post-Baseline Vital Signs

Vital Parameter	Sign	Abnormally Low	Abnormally High
Heart Rate (bpm)		A decrease from Baseline of ≥ 20 to a value ≤ 50	An increase from Baseline of ≥ 20 to a value ≥ 110
Systolic blood pressure (mmHg)		A decrease from Baseline of ≥ 20 to a value ≤ 90	An increase from Baseline of ≥ 20 to a value ≥ 180
Diastolic blood		A decrease from Baseline of	An increase from Baseline of

pressure (mmHg)	≥ 20 to a value ≤ 50	≥ 20 to a value ≥ 105
Body weight (kg)	Loss of $\geq 5\%$	Gain of $\geq 5\%$

Vital sign measurements will be presented by patient, visit and parameter in a data listing.

6.5. Physical Findings

The physical examination will be performed at screening and end of study (or early termination) and the results will only be listed.

6.6. Drug induced bronchospasm

- Drug induced bronchospasm, defined as a decrease from pre-dose FEV₁ value of > 20% within the first hour after dosing.

6.6.1. Analysis of drug induced bronchospasm

The number of patients with at least one event of drug induced bronchospasm will be summarized by counts and percentage, overall and displayed by spirometry assessment (Day 1 and Week 1 to 4). The total number of events will also be displayed.

7. Pharmacokinetic

- Concentration of study medication at pre-dose assessment of Week 1 and Week 4
- Correlation of pre-dose concentration with trough FEV₁ at Week 1 and at Week 4

7.1. Analysis of pharmacokinetic

The concentration of study medication will be summarized at week 1 and 4. The correlation with the pre-dose FEV₁ value will be presented in a graphical representation. Pearson's correlation and its 95% CI will be presented as well.

Abbreviations: BDI=Baseline Dyspnea Index; ECG=electrocardiogram; ICS=inhaled corticosteroids; MRC=Medical Research Council; QTcF=QT interval corrected using Fridericia's formula; PGAC=Patient Global Assessment of Change; PK=pharmacokinetics; SGRQ-C=St George's Respiratory Questionnaire-COPD specific; TDI=Transition Dyspnea Index

(a) Informed Consent may be obtained prior to screening visit
(b) Serum pregnancy test at Visit 1; urine pregnancy test at Visits 2-6
(c) At Visit 2, study medication is to be administered at the study clinic twice; first, just after randomization and again 12 hours later once all assessments are complete
(d) Spirometry at Visits 2 and 6 is performed 15 minutes pre-dose, followed by 30 minutes and 1, 2, 3, 4, 6, 8 and 12 hours post-dose
(e) Spirometry at Visits 3, 4, and 5 are performed 15 minutes pre-dose, followed by 30 minutes and 1, 2, and 3 hours post-dose
(f) Vital signs at Visits 2 and 6 are measured pre-dose and 30 minutes, 1, 2, 4, 6, 8, and 12 hours post-dose
(g) Vital signs at Visits 3, 4, and 5 are measured pre-dose and 30 minutes, 1, 2 and 3 hours post-dose
(h) ECG at Visits 2 through 6 is performed pre-dose and 2 hours post-dose
(i) BDI administered at Visit 2, TDI administered at Visits 4 and 6
(j) A second canister of albuterol/salbutamol may be dispensed during the study if necessary
(k) Holter is to be removed 24 hours (± 1 hour) after placement

9.2. Appendix 2: EXACT-PRO and E-RS Scoring Instructions

The following instructions are from the user manual for EXACT-PRO, version 7.0 (EXACT-PRO Initiative, 2014)

- Raw scores are assigned to each item response option as shown in Table 7 below. Please note that items 3, 8, 9, 10, 11 and 14 have separate scoring instructions, namely with the same raw score being assigned to several answer options.
- Sum the item-level raw scores of the 14 EXACT items to form the raw summed score
- For each raw summed score, look up the corresponding EXACT Total score from Table 6 below.

Notes:

1. EXACT total scores range from 0 to 100
2. If the EXACT total score is 0, set to missing.
3. The Evaluating Respiratory Symptoms (E-RS) part of the EXACT tool consists of the first 11 items, broken down as follows (Evidera, 2014):
 - a. RS-Breathlessness: items 7, 8, 9, 10 and 11 (score range: 0-17);
 - b. RS-Cough & Sputum: items 2, 3 and 4 (score range: 0-11);
 - c. RS-Chest Symptoms: items 1, 5 and 6 (score range: 0-12).

Scoring the domains:

The following respiratory domains are included in the EXACT measure: Breathlessness, Cough/Sputum and Chest Symptoms.

Items are assigned to specific domains as follows (please note that items 4, 12, 13 and 14 do not correspond to a domain and hence, are not used in domain-specific analyses):

- Breathlessness: items 7, 8, 9, 10 and 11
- Cough and Sputum: items 2 and 3
- Chest Symptoms: items 1, 5 and 6

Score the domains as follows:

- For each day, sum the item-level raw scores of the items comprising the domain to form the domain raw summed score. If no diary entry exists for a given day, leave the domain raw summed score missing.
- For each domain raw summed score, look up the corresponding EXACT domain score from Table 7
- If no diary entry exists for a given day, leave the EXACT domain score missing.
- If the daily EXACT domain score is 0, set it to missing.

Table 5: Annotated EXACT for raw score assignment

1. Did your chest feel congested today?	0. Not at all
	1. Slightly
	2. Moderately
	3. Severely
	4. Extremely
2. How often did you cough today?	0. Not at all
	1. Rarely
	2. Occasionally
	3. Frequently
	4. Almost constantly
3. How much mucus (phlegm) did you bring up when coughing today?	0. None at all
	1. A little
	1. Some
	2. A great deal
	3. A very great deal
4. How difficult was it to bring up mucus (phlegm) today?	0. Not at all
	1. Slightly
	2. Moderately
	3. Quite a bit
	4. Extremely
5. Did you have chest discomfort today?	0. Not at all
	1. Slight
	2. Moderate
	3. Severe
	4. Extreme
6. Did your chest feel tight today?	0. Not at all
	1. Slightly
	2. Moderately
	3. Severely
	4. Extremely
7. Were you breathless today?	0. Not at all
	1. Slightly
	2. Moderately
	3. Severely
	4. Extremely
8. Describe how breathless you were today	0. Unaware of breathlessness
	1. Breathless during strenuous activity
	2. Breathless during light activity
	3. Breathless when washing or dressing
	3. Present when resting
9. Were you short of breath today when performing your usual personal care activities like washing or dressing?	0. Not at all
	1. Slightly
	2. Moderately
	3. Severely
	3. Extremely
	4. Too breathless to do these

10. Were you short of breath today when performing your usual indoor activities like cleaning or household work?	0.Not at all
	1.Slightly
	2.Moderately
	3.Severely
	3.Extremely
11. Were you short of breath today when performing your usual activities outside the home such as yard work or errands?	3.Too breathless to do these
	0.Not at all
	1.Slightly
	2.Moderately
	3.Severely
12. Were you tired or weak today?	3.Extremely
	3.Too breathless to do these
	0.Not at all
	1.Slightly
	2.Moderately
13. Last night, was your sleep disturbed?	3.Severely
	4.Extremely
	0.Not at all
	1.Slightly
	2.Moderately
14. How scared or worried were you about your lung problems today?	3.Severely
	3.Extremely
	0.Not at all
	1.Slightly
	2.Moderately

Table 6: Raw Summed Score to Scale Conversion Table for EXACT Total Score

Raw Score	Summed	EXACT Score	Total	Raw Score	Summed	EXACT Score	Total
0		0		26		50	
1		8		27		51	
2		13		28		52	
3		17		29		53	
4		20		30		54	
5		23		31		55	
6		25		32		57	
7		27		33		58	
8		28		34		59	
9		30		35		60	
10		31		36		61	
11		33		37		63	
12		34		38		64	
13		36		39		65	
14		37		40		67	
15		38		41		68	
16		39		42		70	
17		40		43		72	
18		41		44		73	
19		42		45		75	
20		43		46		77	
21		44		47		80	
22		46		48		83	
23		47		49		87	
24		48		50		92	
25		49		51		100	

Table 7: Raw Summed Score to Scale Score Conversion Table for EXACT Domains

Domain Raw Summed Score	Breathlessness Domain Score	Cough & Sputum Domain Score	Chest Symptoms Domain Score
0	0	0	0
1	11	13	12
2	19	25	23
3	25	39	31
4	30	56	38
5	34	72	45
6	38	86	52
7	42	100	58
8	45		65
9	48		72
10	52		79
11	56		88
12	60		100
13	65		
14	71		
15	78		
16	87		
17	100		

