5.5.2. Symptom Diary [EXACT-PRO]

Once patients provide answers to all 14 questions on the ePRO, the device produces a score for each of three subscales: breathlessness, cough/sputum and chest symptoms. In addition to the subscale scores, a total score (covering all 14 questions) and a score for the E-RS part (11 questions) together with the subscores will be obtained.

The average over the week 1, 2, 3 and 4 will be used as timepoint values, while the one over the week just prior to randomization (visit 2) will be used as baseline. If less than 4 days are available, the average over that week is set to missing.

Scoring will be performed as described in Appendix 2: EXACT-PRO and E-RS Scoring Instructions .

Note that, as the data are collected with an e-diary, there is no possibility of having missing items in the questionnaire as the system does not allow the patient to skip items.

Also note that the EXACT-PRO subscale scores are not endpoints of the study but will be summarized for eventual comparison with other published studies

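### SAP Appendix 2 sets an EXACT total score of 0 from a completed diary to missing, which can shrink the EXACT Total effect of an arm with more zero-score days than placebo

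*SAP*

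**What the plan says.** Appendix 2 of the SAP (section 9.2) sets out EXACT scoring and attributes it to version 7.0 of the instrument's user manual. Note 1 states "EXACT total scores range from 0 to 100". Note 2 states "If the EXACT total score is 0, set to missing". Table 6 ("Raw Summed Score to Scale Conversion Table for EXACT Total Score") converts a raw sum of 0 to a score of 0 and a raw sum of 1 to a score of 8.

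For the EXACT domains the appendix has two separate instructions. One covers absent diaries: "If no diary entry exists for a given day, leave the EXACT domain score missing". The other covers completed ones: "If the daily EXACT domain score is 0, set it to missing".

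SAP 5.5.2 says of the e-diary that "there is no possibility of having missing items in the questionnaire". It uses weekly averages as the time-point values and adds: "If less than 4 days are available, the average over that week is set to missing".

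Change from baseline in EXACT Total is a secondary endpoint at Week 4 (SAP 5.2) and exploratory at Weeks 1 to 3 (SAP 5.3). It is analysed by the same MMRM as the primary endpoint (SAP 5.6.3). Under SAP 3.8.1 there is no further imputation, and LOCF is reserved for the primary endpoint. Protocol 9.2.2.5 describes daily and weekly EXACT-PRO scoring without excluding zeros, and the list of changes in SAP 3.4 does not mention the rule.

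**The concern.** If items cannot be skipped, a total of 0 can arise only when the patient answered all 14 items and chose the lowest category each time. That is the best possible report, not an absent one, yet the rule treats it as if no diary had been kept.

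Two things follow. A week with a few zero days is averaged over its worse days only. A week with too many zero days has no value at all. In both cases what is removed is decided by the score itself. An MMRM gives valid estimates when missingness depends on observed data; it does not correct for values deleted because they were low. No planned sensitivity analysis covers this endpoint.

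At stake is the comparison of each dose with placebo on EXACT Total. There is also an inconsistency between related endpoints: the same all-zero diary counts as 0 for the E-RS score, which carries no zero rule, and as missing for EXACT Total.

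**Working it through.** **Is 0 a real score?** The item maxima in SAP Table 5, items 1 to 14, are 4, 4, 3, 4, 4, 4, 4, 3, 4, 3, 3, 4, 4, 3. (The print of items 13 and 14 is broken; they were read as 4 and 3.) They sum to 51, the last raw sum in Table 6, which converts to 100. The floor is raw sum 0, which converts to 0. The scale is internally consistent, and 0 is its lowest point rather than a missing-data code.

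**Which level does Note 2 act on?** It does not say. The parallel domain rule is explicitly daily, so the daily reading is used here.

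**Effect on one week.** Let k be the number of zero days, s the score on each other day, and m the number of days without a diary. With m = 0:

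- zeros kept: mean = (7 − k) × s / 7
- zeros set to missing: mean = s if 7 − k ≥ 4; otherwise the week is missing

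| k | s | Zeros kept | Under the rule |
|---|---|---|---|
| 3 | 8 | 4 × 8 / 7 = 4.57 | 8.00 |
| 3 | 20 | 4 × 20 / 7 = 11.43 | 20.00 |
| 4 | 8 | 3 × 8 / 7 = 3.43 | missing |
| 7 | – | 0 | missing |

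The upward shift in a retained week is k × s / 7; for k = 3 and s = 8 this is 24 / 7 = 3.43 points. With missed diaries, the week is lost once k + m ≥ 4, so a patient with two missed days loses the week after two zero days.

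**Effect on the comparison.** This needs the frequency of zero days, which the documents do not give. A simulation with assumed frequencies shows direction only. It used 100,000 patients per arm and seven diaries each at baseline and Week 4. Latent raw scores were normal, rounded and clipped to 0–51, then converted by Table 6. Week 4 change was analysed by ANCOVA on baseline.

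| Zero days at Week 4, control / active (assumed) | Difference, zeros kept | Difference under the rule | Shrinkage | Patients without a usable change, control / active |
|---|---|---|---|---|
| 1.6% / 3.5% | −2.99 | −2.79 | about 7% | 1.6% / 3.0% |
| 6.7% / 19.0% | −7.57 | −6.61 | about 13% | 6.9% / 18.0% |
| 21.9% / 36.9% | −4.87 | −3.87 | about 20% | 23.4% / 36.0% |

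With no treatment effect, the difference stayed at about 0 under both scorings. The simulation applied the rule at baseline too. Randomisation balances that loss between arms, but it does not cancel the loss after baseline. The model was a single-visit ANCOVA, not the planned MMRM, so the percentages are not estimates for this trial.

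**The case against.** The strongest reply is that the scoring is not the sponsor's invention. The SAP attributes it to the instrument's manual, which cannot be checked here, and replacing it in the main analysis could weaken comparability with other studies. That stands as a reason not to insist on replacement. It does not remove the conflict with the stated range or make the deletion ignorable.

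The second reply is that zero days may be rare. A 0 needs every item at its floor, including cough, mucus, breathlessness, tiredness, sleep and worry. The patients have had symptoms for at least a year, have a post-bronchodilator FEV₁ of 40% to 80% of predicted, and are off long-acting bronchodilators. This also stands: the bias may be small.

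A reader might infer more than the documents support:

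- *Every effective arm is penalised.* Only an arm with more zero-score days than placebo is affected, and an FEV₁ benefit need not produce them.
- *The best responders leave the MMRM.* A patient with a missing Week 4 still contributes any other observed week. The patient leaves entirely only if the baseline week or every post-baseline week is missing.
- *All diary endpoints are affected.* Of the five diary endpoints at Week 4 in SAP 5.2, the rule is stated for EXACT Total alone. The other four are E-RS scores, whose ranges start at 0 and which have no such rule.
- *The domain recode is a further harm to endpoints.* SAP 5.5.2 says the EXACT subscale scores are not endpoints.

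**Conclusion.** The point holds for change from baseline in EXACT Total, at Week 4 and at Weeks 1 to 3. On the daily reading, the rule deletes completed symptom-free diaries, raises the weekly mean when one to three days are 0 (4.57 becomes 8.00 in the example), and removes the week when four or more are. The resulting bias is toward no effect for any arm with more zero-score days than placebo. If Note 2 were meant for weekly averages, only all-zero weeks would be lost: the same direction, but smaller.

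The size cannot be derived from the documents. The simulated shrinkage of 7% to 20% rests on assumed zero-day rates and should not be quoted as the magnitude here. Secondary endpoints are exploratory and tested nominally (SAP 5.6.5), and the rule creates no false-positive risk in the simulated null. The primary FEV₁ analysis and its dose sequence are untouched. This is a cheap improvement to one secondary endpoint, not a threat to the trial's main conclusion.

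**What to change.** In SAP Appendix 2 and section 5.6.3:

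1. State whether Note 2 applies to daily totals or to weekly averages.
2. Keep the manual-attributed scoring for the main EXACT Total analysis if the sponsor wants it.
3. Add an EXACT Total analysis with the same MMRM in which a 0 from a completed diary stays 0 and a day is missing only when there is no diary entry.
4. Report by arm, for baseline and each treatment week, the number of zero-score days and the number of weeks lost to the rule.

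No new data are needed. The cost is one extra analysis and one table, plus a second EXACT Total result that departs from the cited scoring and must be labelled as such. If the counts show few zero days, the two results will nearly coincide and the question is closed.
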